Supervision and limit setting: Parents are given information and practice opportunities for managing behavior in toddler years, ignoring unwanted behavior, setting limits, and keeping the home a safe environment.

Consumer Satisfaction/Exit Interview The 2-page website feedback survey administered at the end of the pilot study asks questions about acceptability, usability of the FCU Online as well as questions about working with a Family Consultant, and suggestions for improvement to the study procedures/content (see attachment "Rural Opioid website satisfaction survey and exit interview"). The consumer satisfaction/exit interview will take approximately 20 minutes.

3. Clinical trial research study (n=400 parents).

After incorporating feedback from the pilot study to materials and process, we will begin the clinical trial phase of the study, where we will recruit 400 English or Spanish speaking families with a child between the ages of 18 months and 5 years old. Two hundred families will be randomly assigned to an intervention condition where participants complete four phone interviews/ surveys over the course of a year and receive the FCU along with coaching from a Family Consultant; two hundred families will be randomly assigned to a control condition where participants complete four phone interviews/surveys over the course of a year and are given access to the FCU at the conclusion of their study participation (e.g., one year later). A quick completion bonus of \$25 will be offered to families at each wave of data collection, if they complete a phone interview or survey within 2 weeks of it being offered to them. Families in the control condition will not receive coaching from a Family Consultant. All families will also be invited to opt into using the EARS tool, which is installed on the participant's phone and collects passive data to record naturalistic behavior related to mental health. Parents will have the opportunity to receive up to \$425 in one year for participating in the study or up to \$400 if they opt out of the EARS component. All research activities will be available to be conducted in either English or Spanish, depending on the preference of each family.

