Official Title: "Rural Families Affected by Opioid Use: An Online Parenting Intervention"

And

"Supplement to Prevention Research Center: Parenting Among Women Who are Opioid Users, Project 2"

NCT Number: NCT05180487

Document Date: 9.20.2019

Document: Statistical Analysis Plan

DATA MANAGEMENT AND ANALYSIS

Data analyses and management will be supported in collaboration with the Data Science Core of the PWO Prevention Center, and will rely on resources and support from the center to test complex models associated with the specific aims of the project as well as management of data in the context of the larger dataset associated with the Center. Data management systems similar to those used in our other web-based research projects will be used to ensure the integrity of the analytic results. These systems entail the creation of scheduling algorithms and web-based data collection forms for each instrument. The collection system contains backup and protection routines that ensure confidentiality and preservation of the electronic records.

We will use accepted practices for handling missing data when appropriate. Maximum likelihood methods with time as a random variable, such as the mixed-effects regression models described below, allow the use of all available data and reduce bias associated with attrition and increasing power. These procedures can provide unbiased conclusions even with substantial attrition. We anticipate a participation rate through 12-month follow-up of at least 85% based on our previous FCU school-based efficacy trials and our current rate of participation and retention in our FCU Online randomized trial.

We will compare baseline characteristics of participants across conditions to test for significant differences; characteristics that differ across conditions will be used as covariates in subsequent analyses. Logistic regression analyses will be used to examine potential differences by study condition between dropouts and continuing participants on baseline measures. Attrition analyses will provide information about the external validity of the study, and interaction effects between condition and predictors will provide information about potential confounding effects.

AIM 1: WORK WITH COMMUNITY STAKEHOLDERS IN RURAL OREGON TO EXPAND THE FCU ONLINE TO TARGET EARLY CHILDHOOD (AGES 2-5) AND MOTHERS WITH OPIOID USE AND ADDICTION.

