We will assess participant quantitative ratings during the usability testing phase in which the benchmark for acceptable ratings will be mean ratings of 4 or greater on a 5-point scale for each of the SUS items and an overall SUS rating of 80.3, which represents an "A" score. Program acceptability will also be demonstrated by (a) a high level of program usage (e.g., 80% of participants complete the FCU assessment and feedback sessions), and (b) a high degree of consumer satisfaction (e.g., mean ratings > 4 on a 5-point rating scale across satisfaction domains).

AIM 2. EXAMINE THE EFFICACY OF FCU ONLINE FOR RURAL FAMILIES WITH OPIOID USE: MAIN EFFECTS, MEDIATORS, AND MODERATORS.

RESEARCH HYPOTHESES. The hypotheses tested in this aim are (a) families in the intervention condition will show significant improvements on the primary outcomes (child problem behavior and school readiness) and secondary outcomes (parenting skills, parent self-regulation/executive control, and child self regulation/ executive control), compared with families in the control condition; and (b) the putative intervention mechanisms of parenting skills and child self-regulation will mediate (either partially or fully) the association between study condition and the longitudinal trajectories of the primary outcomes. Though we have no specific hypotheses regarding moderating mechanisms, we will also conduct exploratory analyses to examine potential moderators of intervention effects. See Statistical Design component of this proposal for additional information.

We will test whether change in the putative mediating mechanisms of parenting skills and self-regulation (e.g., baseline to 3 months) mediate the association between study conditions and longitudinal trajectories of the primary child outcomes (e.g., overall trajectories, 3- to 12-month change to establish temporal precedence of mediators). Such mediating effects will be tested using the strategies outlined by MacKinnon and Preacher and Hayes. We will assess the joint significance of the indirect pathways (i.e., the joint significance of the pathways from the predictor to the mediating variable and from the mediating variable to the outcome) using the bias-corrected bootstrap test, as recommended by Fritz and MacKinnon. We will also use the bootstrapping technique to test multiple simultaneous mediators proposed by Preacher and Hayes.

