The moderation analyses will follow recommendations by Kraemer and colleagues and analytic methods of Aiken and West, Jaccard and Turrisi, and Preacher et al. Each of the potential moderating effects (e.g., child biological sex, race/ethnicity, SES, service utilization; and neonatal abstinence syndrome) will be investigated by conducting the above-mentioned mixed-effects analyses for each outcome that incorporate the Moderator \times Condition interaction term. We have no specific hypotheses for testing sex as a biological variable that would impact outcomes, but we will include sex as a moderator in these analyses. For example, we will test for individual differences in the effect of intervention response (e.g., child problem behavior trajectories) as a function of the participant's value of baseline moderator. Significant moderating effects will be further probed to understand the nature of the conditional relation using computational tools recommended by Preacher et al.

SAMPLE SIZE AND POWER. Using an intent-to-treat approach for the hypothesis of an overall intervention effect, with 127 participants per condition after accounting for 15% attrition across the 12-month assessment period, alpha set to .025 (to adjust for the two outcome domains), there is sufficient power ($>.80$) to detect a condition effect of Cohen's d = .30 or larger. Previous FCU efficacy trials have demonstrated medium-to-large effects for antisocial cigarette use, alcohol use, cannabis use, antisocial behavior, and family conflict. As reported in the prior research section, initial analyses of our ongoing efficacy trial of the FCU Online program demonstrated a medium effect size ($d = .45$) for improvements in child health behaviors, and small-to-medium effect sizes for child social/emotional behavior ($d = .35$), parenting self-efficacy and confidence ($d = .37 - .41$). Given that the effect sizes obtained in the previous FCU efficacy research and the FCU Online preliminary analyses are larger than the power estimates, we should be sufficiently powered to detect meaningful differences between study conditions.

AIM 3. EXAMINE FACTORS RELATED TO SUCCESSFUL UPTAKE AND IMPLEMENTATION.

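### The SAP adds covariates when a baseline characteristic differs significantly between randomised arms; a short set named in advance for prognostic value would be a minor, cheap improvement.

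*SAP*

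**What the plan says.** The protocol (section C, clinical trial research study) describes individual randomisation: "Two hundred families will be randomly assigned to an intervention condition", with an equal number assigned to control.

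The SAP (Data Management and Analysis) sets a two-step rule. First, "We will compare baseline characteristics of participants across conditions to test for significant differences". Second, "characteristics that differ across conditions will be used as covariates in subsequent analyses". It gives no test level and no list of the characteristics to be tested.

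The main-trial model is only pointed to. The missing-data paragraph refers to "Maximum likelihood methods with time as a random variable, such as the mixed-effects regression models described below". The Aim 2 hypotheses speak of "the association between study condition and the longitudinal trajectories of the primary outcomes" and add: "See Statistical Design component of this proposal for additional information". The moderation paragraph relies on "conducting the above-mentioned mixed-effects analyses for each outcome". The posted text sets out such models only for the supplement, where the pilot comparison adjusts for the pre-test value of each target. For Aim 2 the only baseline variables named are candidate moderators: "child biological sex, race/ethnicity, SES, service utilization; and neonatal abstinence syndrome".

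**The concern.** Adjustment in a randomised trial is useful when the covariate predicts the outcome. Significance of a baseline difference says nothing about that. When allocation is random, any tested characteristic enters with probability equal to the test level, whether it is strongly prognostic or irrelevant. Two things follow. The part of the model governed by this rule is unknown until the baseline data are seen, and the unstated test level and candidate list leave the analyst room to choose. A covariate that could sharpen the estimate is also left out most of the time. Because the rule feeds all later analyses, the same chance-dependent set is carried through the primary and secondary outcomes.

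**Working it through.** **The plan's own figure.** The SAP gives no figure for this rule. The nearest is the Aim 2 power statement: above .80 for d = .30 with 127 per condition at alpha .025. A plain two-sample comparison has SE = √(2/127) = .1255 and two-sided critical value 2.241, so power = Φ(.30/.1255 − 2.241) = Φ(.149) = .559. Reaching .80 at one time point needs a baseline-outcome correlation of at least .63, or else averaging over follow-ups. The documents do not state which is meant. So the check is run with the baseline outcome in the model.

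**Inputs.** From the SAP: 127 per arm, d = .30, alpha .025 (taken as two-sided). From the protocol: four waves (baseline, 3, 6 and 12 months). Assumed, because the documents are silent: a correlation of .6 between any two waves, complete data, one extra covariate with correlation *a* to every wave, and a .05 test for entry.

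**Entry by chance.** A given covariate enters in 5% of trials at a .05 test and 10% at a .10 test. If only the five named moderators were tested and they were independent, there would be 2⁵ = 32 possible sets. At least one would enter in 1 − .95⁵ = 23% of trials (1 − .90⁵ = 41% at .10). That candidate list is itself an assumption.

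**Gain from a fixed covariate, 12-month contrast.** With the baseline outcome (correlation r = .6) and the covariate both in the model, R² = (r² + a² − 2ra²)/(1 − a²), and power = Φ(.30/[.1255·√(1 − R²)] − 2.241).

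- No covariate: R² = .36, power .772.
- a = .3: R² = (.36 + .09 − .108)/.91 = .376, power .784.
- a = .5: R² = (.36 + .25 − .30)/.75 = .413, power .810.

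**Rule against fixed adjustment.** These results come from simulation (400,000 trials per cell). Values run about half a point below the formula because t-tests are used.

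| Correlation *a* | 12 months: rule | 12 months: always adjusted | Mean of 3 follow-ups: rule | Mean of 3 follow-ups: always adjusted | Type I error under rule, 12 months |
|---|---|---|---|---|---|
| .1 | .767 | .766 | .950 | .950 | .025 |
| .2 | .767 | .770 | .950 | .953 | .025 |
| .3 | .767 | .776 | .951 | .957 | .025 |
| .5 | .770 | .804 | .953 | .974 | .024 |

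At a = .3 the loss is .776 − .767 = .9 point (12 months) or .957 − .951 = .6 point (mean). At a = .5 it is .8045 − .7700 = 3.45 points or .9745 − .9533 = 2.1 points. At 170 per arm (200 × .85) and a = .3, the formula gives .888 without and .896 with the covariate, so the gain is again under one point.

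**When the covariate does enter.** The 12-month estimate moves on average by .015, .024, .035 or .058 SD (a = .1, .2, .3, .5). The significance verdict then differs in 5%, 8%, 11% or 17% of those trials. Entry occurs in 5% of trials, so at most .05 × .173 = .9% of all trials are affected.

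**Free baseline means.** If the 12-month effect is a difference in change from baseline, the SD of change is √(2 × .4) = .894 and power is Φ(.30/[.894 × .1255] − 2.241) = .667. A covariate equally related to every wave cancels from the change. In simulation at a = .3, power was .663 under the rule and .661 with constant adjustment, so nothing is gained.

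**The case against.** The strongest case on the other side has four parts.

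- **The cost may be nil.** The SAP's language of trajectories, with time as a random variable, suggests a condition-by-time model, and nothing posted says that baseline means are constrained equal. With free baseline means the gain disappears for a covariate equally related to every wave. In a random-intercept version with complete data, a main effect of a time-constant covariate does not move the condition-by-time estimate at all. This stands, and it limits the point.
- **The rule may be an addition.** The SAP says that differing characteristics will be used, not that only those will be. A fixed set may sit in the Statistical Design component, which is not among the documents. This also stands. A reader might infer that the whole Aim 2 adjustment set is left to chance, but the documents do not establish that. The test-based part would still need reconciling with any such list.
- **The candidate covariates are unproven.** No document shows that child age or sex predicts these outcomes, and secondary outcomes include parent measures. This stands, so the choice belongs to the team.
- **It may be late.** The SAP is dated September 2019 and the protocol April 2025, while the trial phase was planned to end by summer 2024. Swapping a stated rule for a chosen set after outcomes are known could itself be data-driven. This stands as a condition on how the change is made.

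Two stronger readings are tempting and fail. A reader might infer inflated false positives; the simulated type I error is at or slightly below .025. A reader might also infer a large power loss. For a single follow-up score with no baseline outcome in the model, power is about .56 under the rule against .60, .69 or .86 with a fixed covariate of correlation .3, .5 or .7. The SAP describes repeated-measures models, so those gaps do not carry over.

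**Conclusion.** The point holds as a minor one. The rule selects for chance imbalance, leaves part of the model open until data are seen, and does nothing useful for precision that a prognostic set would not do at least as well. It is not a validity defect. The power loss is zero to about one point up to a covariate correlation of .3 and about two to three and a half points at .5, and it may be nil under free baseline means. These sizes rest on an assumed wave correlation of .6, complete data, one covariate, a .05 entry test and 127 per arm. The main reason to act is that the model would be known in advance; the gain in power is secondary.

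**What to change.** In the SAP's Data Management and Analysis section, delete the test-based rule and put in its place:

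- a short covariate set for each outcome, named in advance and chosen by the team for expected prognostic value (child age and child sex are examples only, and age may add little if scores are age-standardised);
- baseline characteristics tabulated by condition without significance tests;
- adjustment for characteristics that look imbalanced kept as a labelled sensitivity analysis.

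Reconcile this text with any covariate list in the Statistical Design component. If outcomes by condition have already been seen, date the change and label it as made after that.

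The cost is SAP wording and a few degrees of freedom. If the named covariates turn out not to be prognostic, variance grows by roughly (N − 3)/(N − 3 − k). With N = 254 that is about .2 point of power for one useless covariate, .6 for three and 1.0 for five. For the examples given, little or no new data collection should be needed: the child's age range is checked at screening, child sex is already a planned moderator, and a baseline assessment is already scheduled.

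### The mediator-to-outcome path behind hypothesis (b) is not randomised, and the only covariate rule in the supplied text selects on imbalance by arm, which is the wrong criterion for confounding of that path.

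*SAP*

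**What the plan says.** The Protocol (Section C, clinical trial) randomises condition and nothing else: "Two hundred families will be randomly assigned to an intervention condition", and the same number to control.

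Hypothesis (b) in the SAP (Aim 2, Research Hypotheses) is that parenting skills and child self-regulation mediate the effect of condition on the primary child outcomes. The mediator is defined as change: "We will test whether change in the putative mediating mechanisms of parenting skills and self-regulation (e.g., baseline to 3 months) mediate the association" between condition and outcome. The outcome is the trajectory of the primary child outcomes. Two examples are given: overall trajectories, and "3- to 12-month change to establish temporal precedence of mediators". The test concerns "the joint significance of the pathways from the predictor to the mediating variable and from the mediating variable to the outcome", carried out "using the bias-corrected bootstrap test".

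That section names no covariates for the mediation models, no assumption about confounding and no sensitivity analysis. The main-trial covariate rule is in the SAP's opening section, Data Management and Analysis: "We will compare baseline characteristics of participants across conditions to test for significant differences"; then "characteristics that differ across conditions will be used as covariates in subsequent analyses".

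The SAP also points to a Statistical Design component for further information. That component is not in the supplied text.

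**The concern.** Randomisation protects the effect of condition on the mediator and on the outcome. It does not protect the association between mediator and outcome. Families whose parenting improves by month 3 may differ at baseline in depression, substance use or service contact, and the same factors may shape how the child changes afterwards.

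A confounder of that path is defined by its relation to mediator and outcome. The SAP selects covariates by their relation to arm. Under randomisation, a significance test by arm picks any given baseline variable at about the test level, however strongly it drives mediator and outcome.

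Such factors are plausible here. Depressed mood is one of several alternative routes into the trial, alongside binge drinking, drug use and past prescription opioid use (Protocol, Section D, clinical trial), so depression and substance use should vary across the sample. Mental health and substance use are both in the parent survey (Protocol, Section C, Materials).

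At stake is the trial's mechanism claim. Mediation is a stated hypothesis; the SAP reserves the word exploratory for the moderators.

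**Working it through.** The plan gives no error rate or power for mediation, so there is no stated figure to reproduce.

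**Inputs from the SAP (Aim 2, Sample Size and Power)**
- 127 per arm after 15% attrition, that is 150 x .85 = 127.5.
- Mediator effect a = .30 (the design effect size) and a = .40 (the SAP cites d = .37 to .41 for parenting self-efficacy and confidence).

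**Assumptions**
- True mediator-to-outcome effect of zero.
- One standardised baseline factor U, with effect g on mediator change and the same effect on outcome change, g = .1 to .4. The documents give no value for g.
- Baseline comparison by arm at .05 (the SAP gives no level), and mediation tests at two-sided .05.

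**Step 1: how often the rule picks U.** About 5% of trials by design (simulated 4-8%). U is therefore unadjusted in about 95%.

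**Step 2: the spurious path.** With M = aT + gU + e and Y = gU + e, each with variance 1 within arm, the unadjusted mediator coefficient is b = g x g: .01, .04, .09 and .16.

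**Step 3: joint significance in closed form.**
- Condition to mediator: z = a / √(2/127). For a = .30 this is 2.39 (power .67); for a = .40 it is 3.19 (power .89).
- Mediator to outcome: z = b / √((1 − b²)/251), which gives 0.16, 0.63, 1.43 and 2.57. The chance of |z| > 1.96 is .05, .10, .30 and .73.
- Rate under the SAP rule = .95 x (product of the two) + .05 x (first x .05). For a = .30: 3.5%, 6%, 19%, 46%. For a = .40: 5%, 8%, 25%, 62%.

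If the residual variance is set to 1 instead of the total, b = g²/(1 + g²) and a is divided by √(1 + g²). The rates at g = .3 become 16% and 21% (a = .30 and .40), and at g = .4 they become 34% and 48%. Simulations on this scale gave 15-23% and 33-49%. This scaling, together with a, explains the width of the ranges quoted.

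**Step 4: simulation with the SAP rule applied** (600 trials per cell, Monte Carlo standard error up to 2 points; total variance 1). Each entry is joint significance / bias-corrected bootstrap.

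| n per arm, a | g | SAP rule | U always adjusted |
|---|---|---|---|
| 127, .30 | 0 | 4% / 7% | 5% / 7% |
| 127, .30 | .2 | 5% / 8% | 4% / 8% |
| 127, .30 | .3 | 18% / 25% | 4% / 8% |
| 127, .30 | .4 | 47% / 57% | 3% / 6% |
| 127, .40 | .2 | 8% / 14% | 4% / 8% |
| 127, .40 | .3 | 25% / 33% | 6% / 10% |
| 127, .40 | .4 | 64% / 70% | 4% / 8% |
| 170, .30 | .3 | 31% / 38% | 4% / 7% |
| 170, .30 | .4 | 69% / 75% | 4% / 8% |

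The 170 rows use the Protocol's 400 families (400 x .85 / 2). More participants make the error more likely, because b does not shrink. The bootstrap sits at 7-8% with no confounder at all, so not all of its excess over 5% is confounding.

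**Step 5: limits.**
- If condition does not move the mediator (a = 0), the rate is at most 4%.
- If U shifts levels equally at every visit, change scores remove it (3% by joint significance). U must affect change: slopes of .2, .3 and .4 on change gave 6%, 16% and 38%.

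**Step 6: would replacing change by the 3-month mediator value help?** With a stable unmeasured trait loading .4 to .7 on every visit, a = .40 and no true mediator effect, change scores gave 3-5%. The 3-month mediator adjusted for baseline mediator and baseline outcome gave 43-95% when the outcome was the 12-month level, and 4-5% when the outcome was 3- to 12-month change.

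**The case against.** **The plan orders mediator and outcome in time.** It does, but only as one of two examples, and time order rules out reverse causation, not a common baseline cause. What stands is that the factor must drive mediator change in months 0-3 and also outcome change in months 3-12, which is a more demanding condition.

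**The covariates may be in the Statistical Design component.** They may. The finding is limited to the supplied text, and the sponsor should confirm. Two other passages do not fill the gap: the SAP's remark on confounding in its opening section concerns attrition analyses, and its control for baseline levels belongs to the supplement pilot.

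**The sizes rest on assumed confounder strengths.** This stands. At .1 there is no inflation and at .2 it is small. A reader might take the top of the range as the trial's error rate, but no figure in the documents supports .4 over .2.

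**The SAP uses a raw difference score, so the baseline level stays in the mediator.** A reader might infer this, but the SAP says only change. A slope or a residualised change would fit that word equally well, so no criticism is built on it.

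**Every trial mediation analysis has this limitation.** True of the unrandomised path. Here, though, a stated covariate rule uses the wrong criterion, and that can be corrected.

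**Conclusion.** The concern holds as a possibility, not a prediction. On the supplied text, a given baseline common cause of mediator change and outcome change goes unadjusted in about 95% of trials and can then be reported as mediation. With 127 per arm and a = .30 to .40, false mediation by joint significance is near nominal at a confounder effect of .1, slightly raised at .2, about 15-25% at .3 and 33-64% at .4. The planned bootstrap runs higher. These figures need three conditions: the program moves the mediator, the factor affects change as well as level, and its strength is as assumed.

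A reader might go further and conclude that the efficacy result is compromised, or that any positive mediation result would be spurious. The documents support neither. The overall condition effect is a randomised comparison and is not biased by this issue, and a real indirect effect remains possible. The SAP calls the mechanisms putative and does not claim proof. The point is worth acting on because the hypothesis is stated in advance and the remedy is cheap.

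**What to change.** First confirm whether the Statistical Design component lists mediation covariates. If it does not, amend the Aim 2 mediation text as follows:

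- Pre-specify baseline parental depression or mental health, baseline substance use and child age as covariates in both the mediator and the outcome equation, regardless of balance by arm.
- Keep the change-based mediator and make 3- to 12-month outcome change the primary mediation outcome. Do not switch to a 3-month mediator value predicting a 12-month level, which can add bias from a stable unmeasured trait (Step 6).
- Add a sensitivity analysis giving the residual mediator-outcome correlation at which the indirect effect becomes zero. This also covers unmeasured and post-baseline confounding. The latter matters because the wellness module itself addresses depression (Protocol, Section C), which baseline adjustment cannot capture.
- State the no-unmeasured-confounding assumption, and report a positive result as consistent with mediation under it.

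Cost: SAP wording and a modest amount of extra analysis. Mental health and substance use are already in the survey, and child age bears on eligibility. The downside is a few degrees of freedom and a more cautious claim.

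### The SAP's mediation test is named in two incompatible ways, and the bias-corrected bootstrap exceeds an assumed 5% level (about 6–7.6%) when one path is null and the other moderate

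*SAP*

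**What the plan says.** Hypothesis (b) of Aim 2 in the SAP is that parenting skills and child self-regulation carry part or all of the effect of condition on the primary outcome trajectories. The analysis sentence opens with "We will assess the joint significance of the indirect pathways" and explains in parentheses that this means the path from condition to mediator together with the path from mediator to outcome. The same sentence ends by naming the procedure: "using the bias-corrected bootstrap test", with a methodological citation. The next sentence plans a bootstrap for several mediators at once without saying which kind of interval.

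No alpha, confidence level, number of resamples or multiplicity rule is given for mediation. The alphas that do appear belong elsewhere: .025 for the overall intervention effect (Aim 2, Sample Size and Power), .05 for the Aim 3 process analyses, and .05 for the supplement pilot.

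On sample size, the SAP works "with 127 participants per condition after accounting for 15% attrition across the 12-month assessment period", so N = 254. The protocol (section C, clinical trial) is larger: "Two hundred families will be randomly assigned to an intervention condition", with as many in the control condition.

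**The concern.** The joint-significance test declares mediation when path a (condition to mediator) and path b (mediator to outcome, given condition) are each significant. The bias-corrected bootstrap declares it when an adjusted interval for the product a×b excludes zero. Two analysts following the one sentence could reach opposite conclusions from the same data.

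The two tests also differ in error rate. When one path is real and the other is zero, the bias-corrected interval is too short on one side and excludes zero too often. One such case matters here: the programme improves parenting, but parenting does not drive the child outcome. A false positive there would be reported as support for the programme's mechanism.

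**Working it through.** **Plan's own figure.** There is none to reproduce, because the SAP gives neither an error rate nor power for mediation. Its stated power concerns the overall condition effect, and only its sample size is used here.

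**Inputs.**
- N = 254, two arms of 127 (SAP, Aim 2, Sample Size and Power).
- Sensitivity case N = 340: 200 per arm (protocol) × .85 retention (SAP) = 170 per arm.
- Path a: the SAP quotes d = .37–.41 for parenting self-efficacy and confidence from the ongoing FCU Online trial. This is the nearest figure to a planned mediator. A range around it was run.
- Assumed, because the documents are silent: two-sided 5% (2.5% as a variant), all values of b, normal errors and a single mediator.

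**Model.** M = a·X + e₁ and Y = b·M + e₂, with unit-variance errors and X the 1:1 condition. The indirect effect is null if a = 0 or b = 0.

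**Tests, on the same simulated data.**
- Joint significance: both t-tests reject.
- Percentile bootstrap: the 2.5% and 97.5% quantiles of the resampled a×b exclude zero.
- Bias-corrected bootstrap: z₀ = Φ⁻¹(share of resampled a×b below the estimate); the quantiles at Φ(2z₀ ± 1.96) exclude zero.

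**Hand check of the joint test.** With one path null, its rate is about .05 × the power of the other path.
- Both null: .05 × .05 = .0025, or 0.25% (simulated 0.26%).
- a = .40, b = 0: SE = √(2/127) = .1255; .40/.1255 = 3.19; power ≈ Φ(3.19 − 1.96) = .89; .05 × .89 = 4.45% (simulated 4.45%).

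**Rejection of a true null, N = 254, nominal 5%** (20,000 trials per cell, 2,000 resamples; Monte Carlo SE at 7.2% is √(.072 × .928/20,000) = 0.18 points):

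| a | b | Bias-corrected | Percentile | Joint |
|---|---|---|---|---|
| 0 | 0 | 0.5% | 0.2% | 0.3% |
| 0 | .10 | 3.1% | 1.2% | 1.8% |
| 0 | .14 | 4.9% | 2.4% | 2.9% |
| 0 | .20 | 7.2% | 4.2% | 4.5% |
| 0 | .30 | 7.0% | 5.1% | 4.9% |
| 0 | .39 | 6.3% | 5.0% | 5.0% |
| 0 | .59 | 5.9% | 5.3% | 5.1% |
| .30 | 0 | 5.8% | 2.8% | 3.3% |
| .35 | 0 | 6.7% | 3.7% | 4.0% |
| .40 | 0 | 7.2% | 4.3% | 4.5% |
| .45 | 0 | 7.6% | 4.6% | 4.7% |
| .50 | 0 | 7.6% | 5.1% | 5.0% |
| .80 | 0 | 6.4% | 5.3% | 5.0% |

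For weaker a with b = 0, a 6,000-trial run gave 1.2% (a = .10) and 3.3% (a = .20) for the bias-corrected test. A separate simulation agreed: .074 and .076 at a = .40 and .45 with b = 0, .071 at a = 0 and b = .20, and .004 with both paths null.

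**Variants.** At nominal 2.5% the bias-corrected test peaks at 4.1%, against at most 2.8% (percentile) and 2.6% (joint). At N = 340 (4,000 trials, 1,000 resamples, SE about 0.4 points) the pattern is the same: 0.4% with both paths null and a peak of about 7.7%.

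**Power at a = .40, b = .20.** One run gave .86 (bias-corrected), .79 (joint) and .78 (percentile). Another gave .84 for the bias-corrected test against .78.

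**The case against.** The SAP names a recognised method with a source. Its first clause can be read as loose wording for testing the indirect effect as a whole. The method offers more power, mediation is a mechanism hypothesis rather than the efficacy test, and the excess is at most about 2.6 points. All of that stands, and it is why the point is not a major one. It does not settle which test decides, since the SAP's own parenthesis describes the two-path test. The extra power also comes with an error rate above the level where one path is moderate.

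Three stronger readings are tempting, and the documents do not support them.

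- A reader might infer that mediation is tested above its level in general. It is not. The test is conservative with both paths null or the non-null path weak, and the 5% level is itself an assumption.
- A reader might infer that the SAP expects d = .35–.45 on its mediators. Those are preliminary results from another FCU Online trial. The .45 is for child health behaviors and the .35 for child social/emotional behavior, neither a planned mediator. No effect size is given for child self-regulation. The SAP hypothesises that both paths are real.
- A reader might compound the excess over two mediators and two outcomes. That would treat tests in the same families as independent. Four independent tests held exactly at 5% already give 1 − .95⁴ = 18.5%, so most of any such total is multiplicity, a separate question.

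**Conclusion.** The point holds in conditional form. The SAP describes one test, names another, and gives neither an alpha. If the named test is used at 5%, it rejects a true null in about 6–7.6% of trials when exactly one path is null and the other moderate, and in about 7% when path a equals the cited parenting effects and b = 0. The two alternatives hold the level to within simulation error. Moving to the protocol's sample size does not remove the excess, nor does adopting 2.5%.

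The figures rest on a cross-sectional single-mediator model with normal errors. The planned models of mediator change and outcome trajectories could shift them somewhat. This is a minor-to-moderate point about the mechanism hypothesis; the main efficacy comparison is unaffected.

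**What to change.** In the Aim 2 mediation paragraph of the SAP:

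1. State the alpha and sidedness for mediation.
2. Declare an indirect effect only if both paths are significant at that alpha, which matches the SAP's own description.
3. Report a percentile bootstrap interval for the size of the effect, and state the number of resamples.
4. Use the same interval type for the multiple-mediator analysis.
5. Remove the bias correction.

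This needs a few sentences and no new data. The price is power: about 6 to 8 points at a = .40 and b = .20 (from .84–.86 to about .78).
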